13.1.3 Adverse Events of Special Interest

An adverse event of special interest (AESI) is one of scientific and medical interest specific to understanding of the Investigational Product and requires close monitoring and rapid communication by the investigator to the sponsor. An AESI may be serious or non-serious. The rapid reporting of AESIs allows ongoing analysis of these events in order to characterize and understand them in association with the use of this investigational product.

13.1.3.1 Hepatic Function Abnormality

Adverse events of hepatic function abnormality of special interest to the sponsor are defined as any increase in ALT or AST to greater than $3 \times$ ULN and concurrent increase in bilirubin to greater than $2 \times$ ULN. Concurrent findings are those that derive from a single blood draw or from separate blood draws taken within 8 days of each other. In the event of hepatic function abnormality where the etiology is unknown, timely follow-up investigations and inquiries should be initiated by the investigational site, based on medical judgment, to make an informed decision regarding the etiology of the event. Investigational product will not be administered to any subject reporting ALT or AST to greater than $3 \times$ ULN and concurrent increase in bilirubin to greater than $2 \times$ ULN

13.1.3.2 Acute and Delayed Hypersensitivity Reactions

Biologic therapies are known to be associated with an increased risk of immediate and delayed hypersensitivity reactions as well as anaphylaxis. Anaphylaxis and severe hypersensitivity reactions are required to be reported within 24 hours of knowledge of the event, [REDACTED]

13.1.3.3 Clinically Significant Pulmonary Abnormality

Any subject who develops new clinically significant pulmonary symptoms or signs should be referred to a qualified specialist for further specific assessment. Symptoms and signs triggering such referral include but are not limited to an increase in shortness of breath or difficulty breathing, exacerbation of current respiratory symptoms, or a significant deterioration in dyspnea score. Subjects who are referred for evaluation by a specialist will undergo a diagnostic evaluation to determine the nature and origin of the pulmonary symptom(s)/sign(s) and to determine if PAP may be present. At the discretion of the investigator or specialist additional tests may be required such as a repeat chest x-ray, and/or a chest high resolution computed tomography scan, full PFTs including DLCO measurement, bronchoscopy with bronchoalveolar lavage, and cytological and/or ultrastructural evaluation of the cells recovered by lavage to identify findings consistent with a diagnosis of PAP. Any subject who has been referred for a specialist pulmonary evaluation may be instructed to stop the investigational product until the symptom(s) or sign(s) causing the referral have resolved.

13.1.3.4 Neutropenia

Adverse events of neutropenia of special interest to the sponsor are defined as an ANC $< 1.0 \times 10^9$ cells/L. Investigational product will not be administered to any subject who has an ANC $< 1.0 \times 10^9$ cells/L. Administration of investigational product may continue in the event that the ANC $> 1.5 \times 10^9$ cells/L and following agreement with the medical monitor.

13.1.3.5 Serious Infection

Grade 3 severity infections that require treatment with IV therapy (antibiotics, antiviral, or antifungal) and opportunistic infections will be considered serious even if they do not require in-patient hospitalization. Every effort should be made to identify the causative pathogen through prompt and appropriate investigation by the investigator or reporting physician.

13.1.4 Adverse Reactions

All noxious and unintended responses to an IMP (i.e., where a causal relationship between an IMP and an AE is at least a reasonable possibility) related to any dose should be considered adverse drug reactions.

13.1.5 Unexpected Adverse Event

An AE or suspected adverse reaction is considered “unexpected” if it is not listed in the current Investigator Brochure or is not listed at the specificity or severity that has been observed. “Unexpected” also refers to AEs or suspected adverse reactions that are mentioned in the Investigator Brochure as occurring with a class of drugs or as anticipated from the pharmacological properties of the drug but are not specifically mentioned as occurring with the particular drug under investigation.

13.1.6 Serious Adverse Event

A serious adverse event (SAE) is any untoward medical occurrence or effect that, at any dose:

- Results in *death* – Includes all deaths, even those that appear to be completely unrelated to study drug (e.g., car accident where subject is a passenger)
- Is *life-threatening* – in the view of the Investigator, the subject was at immediate risk of death from the event at the time of the event (i.e., it does not include an AE that might have caused death if it had occurred in a more serious form).
- Requires *in-patient hospitalization* or prolongs an existing hospitalization. (Complications occurring during hospitalization are AEs and are SAEs if they cause prolongation of the current hospitalization. Hospitalization for elective treatment of a pre-existing non-worsening condition is not, however, considered an AE. The details of such hospitalizations must be recorded on the medical history or physical examination page of the eCRF. Hospitalization is defined as an admission to the hospital ward or a short-stay-type unit longer than 24 hours. Prolongation of existing hospitalization is defined as hospital stay longer than originally anticipated for the event or development of a new AE as determined by the Investigator or treating physician.
- Results in *persistent or significant disability/incapacity* (an AE is incapacitating or disabling if it results in a substantial and/or permanent disruption of the subject’s ability to carry out normal life functions).
- Is a congenital anomaly/birth defect.
- Is an *important medical event* – Important medical events may not be immediately life-threatening or result in death or hospitalization but may jeopardize the subject or may require intervention to

prevent one of the other serious outcomes listed above (e.g., intensive treatment in an emergency room or at home for allergic bronchospasm; blood dyscrasias or convulsions that do not result in hospitalization; or development of drug dependency or drug abuse).

In addition, medical and scientific judgment is required to decide if prompt notification is required in situations other than those defined for SAEs above, i.e., any event that the Investigator regards as serious that did not strictly meet the criteria above but may have jeopardized the subject or required intervention to prevent one of the outcomes listed above, or that would suggest any significant hazard, contraindication, side effect, or precaution that may be associated with the use of the IMP.

All SAEs that occur after signing of study-related informed consent, whether or not the SAEs are related to the study drug or study procedures, must be reported.

13.1.7 Suspected Unexpected Serious Adverse Reaction

A Suspected Unexpected Serious Adverse Reaction is an adverse reaction, the nature or severity of which is not consistent with the applicable product information (e.g. investigator's brochure for an unauthorized investigational product or prescribing information/summary of product characteristics for an authorized product). All relevant information about suspected serious unexpected adverse reactions that are fatal or life-threatening will be recorded and reported to the competent authorities in all the applicable countries, and to the Ethics Committee/Institutional Review Boards in conjunction with Directive 2001/20/EC.

13.2 Adverse Event Assessment

13.2.1 Relationship to Study Drug

The causal relationship between an AE and the study drug will be defined as below:

- **Not Related:** when the AE is definitely caused by the subject's clinical state, or the study procedure/conditions
- **Unlikely Related:** when the temporal association between the AE and the drug is such that the drug is not likely to have any reasonable association with the AE
- **Possibly Related:** when the AE follows a reasonable temporal sequence from the time of drug administration but could have been produced by the subject's clinical state or the study procedures/conditions
- **Related:** when the AE follows a reasonable temporal sequence from administration of the drug, abates upon discontinuation of the drug, follows a known or hypothesized cause-effect relationship, and (if appropriate) reappears when the drug is reintroduced.

13.2.2 Intensity

The severity of an AE will be recorded as one of the following:

- **Mild:** easily tolerated, does not interfere with normal daily activities, does not require intervention
- **Moderate:** causes some interference with daily activities; minimal, local, or noninvasive intervention indicated
- **Severe:** medically significant event; daily activities limited or completely halted; hospitalization or prolongation of hospitalization indicated

Every reasonable effort will be made to follow subjects who have AEs. Any subject who has an ongoing AE at study end or early withdrawal will be followed, where possible, until resolution.

13.3 Recording Adverse Events

Each patient should be monitored for the development of any AEs. This information should be collected by asking nonleading questions (such as “How are you feeling?”) and from observations of and conversations with patients. AEs may also be collected by direct physical exam, diagnostic procedures, or any other appropriate source.

All AEs (serious and non-serious) will be documented in the patient’s source documents and recorded in the eCRF. Any clinically relevant (as determined by the Investigator) deterioration in laboratory assessments or other clinical findings is considered an AE and must be recorded in the patient’s source documents and in the eCRF.

13.3.1 Adverse Events Based on Signs and Symptoms

All AEs spontaneously reported by the patient or reported in response to the open question from the study personnel or revealed by observation will be collected and recorded in the eCRF. When collecting AEs, the recording of a diagnosis is preferred (when possible) to the recording of a list of signs and symptoms. However, if a diagnosis is known and there are other signs or symptoms that are not generally part of the diagnosis, the diagnosis and each sign or symptom will be recorded separately.

13.3.1 Adverse Events Based on Examinations and Tests

If deterioration in a laboratory value/vital sign is associated with clinical signs and symptoms, the sign or symptom will be reported as an AE and the associated laboratory result/vital sign will be considered as additional information. Wherever possible the reporting Investigator uses the clinical rather than the laboratory term (e.g., anemia vs low hemoglobin value). In the absence of clinical signs or symptoms, clinically relevant deteriorations in nonmandated parameters should be reported as AEs.

Any new or aggravated clinically relevant abnormal medical finding at a physical examination as compared with the baseline assessment will be reported as an AE.

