13.1 Adverse Events

13.1.1 Adverse Event Definition

An AE is any untoward medical occurrence in a subject or clinical investigation subject administered a pharmaceutical product. An AE does not necessarily have a causal relationship with this treatment. An AE can therefore be any unfavorable and/or unintended sign (including an abnormal laboratory finding), symptom or disease temporally associated with the use of a medicinal (investigational) product, whether or not related to the medicinal (investigational) product.

AEs also include: any worsening (i.e., any clinically significant change in frequency and/or intensity) of a pre-existing condition that is temporally associated with the use of the study drug; abnormal laboratory findings considered by the reporting Investigator to be clinically significant; and any untoward medical occurrence.

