### **6.8.1. Adverse Events**

An adverse event (AE) is any untoward medical occurrence in a subject or clinical investigation subject administered a pharmaceutical product. An AE does not necessarily have a causal relationship with this treatment. Drug-related AEs will be considered those to be at least possibly related to investigational product based on the investigator's assessment.

Treatment emergent AEs (TEAEs) is defined as AEs that begin after the first administration of investigational products or existing AEs that worsen after the first dose of study medication through the 90 days after the last dose date.

TEAEs will be coded using MedDRA version 21.0. A summary of the frequency (number and percentage of subjects) of TEAEs will be presented by system organ class (SOC) and preferred term (PT) by treatment, in decreasing frequency of SOC and PT in the KPL-301 arm. The TEAE will also be analyzed by their severity (mild, moderate or severe), relationship to study drug, leading to death, resulting in dose interruption, leading to withdrawal of study treatment. Treatment emergent serious AEs (TESAE), drug related TESAEs, TEAE of special interest (TEAESI) will also be tabulated.

An adverse event of special interest (AESI) is one of scientific and medical interest specific to understanding of the Investigational Product and requires close monitoring and rapid communication by the investigator to the sponsor. An AESI may be serious or non-serious. AESI are defined in Section 13.1.3 of the protocol.

A subject experiencing the same AE multiple times will be counted only once for that preferred term. Similarly, if a subject experiences multiple AEs (preferred terms) within the same system organ class, then that subject will be counted only once for that system organ class. When summarizing by severity and relationship, only event with highest severity or relationship will be counted.

Tables will include the following details:

- Overview of TEAEs (summary from all the subsequent tables)
- TEAEs by severity
- Drug related TEAEs
- TESAEs
- Drug related TESAEs
- Non-serious TEAEs
- TEAESI
- TEAEs leading to permanent discontinuation of study drug
- TEAEs leading to dose interruption
- TEAEs resulting in deaths.

All AEs and SAEs occurring throughout the conduct of the study, including all-cause deaths, will be displayed in listings.

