**Other:**

Serum pregnancy test prior to randomization

Urine pregnancy test at Day 0, Week 12, Week 26 and the Final Washout Safety Follow-up Visit.

Continuous laboratory data will be examined for trends using descriptive statistics of actual values and changes from baseline over time in each treatment group. These data will also be categorized as low, normal or high based on the reference ranges of the central laboratory. Shift tables from baseline to worst post baseline time point will be presented. In shift tables from baseline to worst

post-baseline value, the worst value post baseline within a subject will include both scheduled and unscheduled visits. In each shift table, the denominator of the percentage in a cell within a baseline category (e.g., normal) will be the total number of subjects in each treatment group in the category at baseline.

Biochemistry and hematology lab tests will be assessed relative to laboratory normal ranges (low, normal, high). Shift from baseline to the worst grade on study, and from baseline to by visit reference will be presented. Shifts from baseline to worst value on study will be presented for categorical or ordinal lab parameters. Incidence of subjects with laboratory values outside laboratory supplied normal range will also be presented.

All biochemistry and hematology results will be presented in by-subject listings. Urinalysis results will be summarized by categoricals and will also be presented in the listing.

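### Protocol 13.3.1 conflicts with the other AE rules on symptom-free changes in mandated tests, and the SAP has no laboratory-derived count to catch AESIs that go unreported

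*Protocol*

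**What the plan says.** **Protocol, recording of test results.** Section 13.3.1 (Adverse Events Based on Examinations and Tests) deals first with laboratory changes that come with symptoms. It then says: "In the absence of clinical signs or symptoms, clinically relevant deteriorations in nonmandated parameters should be reported as AEs". It does not say what happens to a symptom-free deterioration in a mandated test, and the protocol does not define *nonmandated*.

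**Protocol, general rules.** The AE definition in 13.1.1 includes "abnormal laboratory findings considered by the reporting Investigator to be clinically significant". Section 13.3 says that any clinically relevant "deterioration in laboratory assessments or other clinical findings is considered an AE and must be recorded", with relevance left to the investigator. Neither section separates mandated from other tests.

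**Protocol, AESIs.** Section 13.1.3.4 reads "Adverse events of neutropenia of special interest to the sponsor are defined as an ANC" below 1.0 × 10^9 cells/L. Section 13.1.3.1 reads "Adverse events of hepatic function abnormality of special interest to the sponsor are defined as any increase in ALT or AST"; the cut-offs are above 3 × ULN for the transaminase and above 2 × ULN for a concurrent bilirubin, where concurrent means one draw or draws within 8 days of each other. Neither definition asks for symptoms. Section 13.1.3 requires prompt communication of AESIs to the sponsor, whether or not they are serious.

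**SAP.** Section 6.8.1 tabulates treatment-emergent AESIs as one class of TEAE and adds only that "AESI are defined in Section 13.1.3 of the protocol". Section 6.8.2 plans descriptive statistics, categories against the reference range, shift tables, the incidence of values outside the normal range, and by-subject listings.

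**The concern.** The neutrophil count and the liver profile are scheduled tests. A site that follows the sentence written specifically for test results has a textual basis for filing no AE when such a test worsens without symptoms. A site that follows 13.3 or 13.1.3 would file one.

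The AESI table is built from what sites file. The incidence by arm of the two laboratory-defined AESIs could then depend partly on which sentence a site followed. These are named risks, and 13.1.3.1 and 13.1.3.4 tie each threshold to withholding the investigational product. A low or zero count in the AESI table could not, on its own, be read as absence of cases.

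**Working it through.** No plan figure needs reproducing. The check sets the passages side by side and adds one line of arithmetic for scale.

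1. **Are the tests mandated?** Yes. Protocol 12.6.2 puts the white cell differential in the hematology panel, and 12.6.4 lists AST, ALT and total bilirubin in the liver profile. Table 1 schedules both panels. I take *nonmandated* to mean tests that the protocol does not require.

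2. **What does each rule say about a symptom-free ANC of 0.9 × 10^9/L?**
   - 13.3.1 (examinations and tests): silent. The qualifier *nonmandated* has a purpose only if mandated tests are handled differently.
   - 13.1.1 and 13.3: an AE if the investigator judges it clinically significant or relevant.
   - 13.1.3.4: meets the AESI definition on the number alone.

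   The implication of the first conflicts with the other two.

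3. **Do the broader rules settle it?** Not completely. Those in 13.1.1 and 13.3 turn on investigator judgement, whereas the AESI thresholds are fixed numbers. Section 13.1.3 asks for rapid communication, but the reporting route described in 13.6 is for SAEs.

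4. **Would the SAP count an event that was not filed?**
   - 6.8.1: no, because a treatment-emergent AESI is a reported TEAE.
   - 6.8.2, range categories: an ANC of 0.9 falls in the same *low* cell as a value just under the laboratory's lower limit.
   - 6.8.2, shift tables: these go analyte by analyte, so they cannot show ALT or AST and bilirubin raised together, or on draws within 8 days.
   - 6.8.2, worst grade: a shift to worst grade is named, but no grading scale is given.
   - 6.8.2, listings: the values appear, but they are not counted by arm against a threshold.

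   By contrast, SAP 6.8.6 does apply explicit cut-offs to pulmonary safety: a 20% reduction in PFT and DLCO, and dyspnea bands of below 3, 3–4 and 5 or more.

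5. **Scale.** Planned numbers are about 42 on KPL-301 and 28 on placebo (Protocol 8.6). One subject is 1/42 = 2.4% or 1/28 = 3.6%, so each missed subject lowers the reported incidence by that many percentage points. Two of the five AESI categories in 13.1.3 (2/5) are affected. The documents give no expected rate for either event and no basis for the share of sites that would read 13.3.1 narrowly, so the number missed cannot be estimated.

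**The case against.** The strongest reply is that 13.3.1 is silent on mandated tests and does not exempt them. To leave such an event unreported, a site would have to infer an exemption from silence and set it above 13.1.1, 13.3 and the AESI sections. There are other safeguards:

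- Resuming dosing after an ANC below 1.0 requires agreement with the medical monitor (13.1.3.4).
- A hepatic case of unknown cause calls for follow-up investigation (13.1.3.1).
- A hepatic case judged related to the product goes to the DMC within 1 business day of the sponsor receiving the report (17.1).
- SAP section 5 puts minimum and maximum in every continuous summary, so a very low ANC at a scheduled visit would show in its arm's minimum.

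Much of this stands. A reader might infer that the plan excludes silent events in mandated tests from AE recording, or that they are bound to vanish from the results. The documents do not support either inference: 13.1.1, 13.3 and 13.1.3 cover these events, and the listings hold the values.

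The safeguards do not supply the missing count, however. DMC referral starts only when the sponsor receives a report, and its hepatic trigger also requires a judgement of relatedness. A minimum shows that at least one extreme value occurred, not how many subjects had one. Nor does it link two analytes.

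**Conclusion.** The point holds as an inconsistency plus a missing backstop, and is best labelled a cheap improvement. Protocol 13.3.1 implies something that 13.1.1, 13.3 and 13.1.3 contradict, and the passages must be reconciled. The SAP text shows no laboratory-derived count of either AESI threshold, so the AESI table depends on site filing, and events may be missed in it. Omission is possible, not certain.

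Two of five AESI categories are touched, at about 2.4 or 3.6 percentage points per missed subject. The primary efficacy analysis is not affected.

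This rests on three assumptions: that *nonmandated* means not required by the protocol; that the planned arm sizes approximate the safety set; and that the separate table specifications cited in SAP section 5, which are not available here, contain no such count.

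**What to change.** 1. **Protocol 13.3.1 (examinations and tests).** Reconcile the sentence with 13.3 and 13.1.3, so that recording an AE or AESI does not depend on whether the test is mandated.

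2. **SAP 6.8.2.** Add a table of subjects by arm with any post-baseline value meeting each laboratory definition in 13.1.3: ANC below 1.0 × 10^9/L; and ALT or AST above 3 × ULN with bilirubin above 2 × ULN, on the same draw or within 8 days. Derive it from the central laboratory data, including unscheduled draws. Beside each count, show how many of those subjects also had the event reported as an AESI over the same dates.

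Both parts are needed. Protocol 12.6 says that local laboratory values are not captured for analysis, so an event seen only on a local draw can reach the results only through an AE record.

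The cost is one sentence and one table from data already collected. The thresholds are the protocol's own and no clinical rule changes. The downside is one more output, and AESI-threshold counts may rise slightly in both arms.
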